## Study protocol with statistical analysis plan

### Significance

People with advanced Alzheimer's Disease and Related Dementias (ADRD) commonly experience functional, cognitive, and behavioral symptoms that interfere with eating (mealtime difficulties), resulting in low intake and subsequent malnutrition and dehydration. Among people living with advanced ADRD in residential care settings (residents), 94% are at risk for malnutrition and 66.5% are already malnourished. Malnutrition further leads to increased infection, weight loss, decreased quality of life, and increased morbidity and mortality. Mealtime difficulties can be ameliorated by maximizing resident independence and use of evidence-based, person-centered care approaches, so as to promote food intake and further maintain nutrition and hydration which are fundamental health needs among the aging population with ADRD.

Despite the increased risks and consequences of mealtime difficulties and inadequate intake, residents are not provided with optimal mealtime care. Person-centered mealtime care (PCMC) is individually tailored to residents based on their preferences and levels of independence, in contrast to task-centered mealtime care (TCMC) that focuses on completion of tasks regardless of resident preferences and abilities. The PCMC features individualized, resident-oriented care through adherence to four principles: 1) providing choices and acknowledging preferences, 2) showing respect, 3) supporting independence, and 4) promoting social interaction. Our preliminary studies show that positive staff engagement and social interaction with residents is associated with reduced mealtime difficulties and improved intake. While PCMC is highly recommended, PCMC strategies haven't been empirically tested using experimental designs. A gap exists in creating effective individualized PCMC interventions to optimize mealtime care quality and resident outcomes.

### Objectives

This study developed and refined OPTIMAL, and evaluated its feasibility, fidelity, and usefulness. The specific aims are:

- 1. Develop, evaluate, and refine OPTIMAL intervention protocol and training materials.** We will integrate evidence from literature and our prior work to develop the intervention protocol and training materials, addressing resident mealtime difficulties, targeted PCMC strategies, and establishment of individualized PCMC plans. We will conduct separate focus group interviews of staff and family participants on the acceptability and appropriateness of the intervention protocol and training materials before pilot testing. Data obtained will be used to refine the intervention protocol and training materials before pilot testing.
- 2. Determine feasibility, fidelity, and usefulness of OPTIMAL.** Feasibility on participant identification, recruitment, consent, and retention will be evaluated descriptively. Fidelity will be assessed on a) delivery of treatment (staff attendance to training sessions), b) receipt of treatment (staff knowledge and self-efficacy post-training), and c) enactment of treatment skills (quality of staff engagement). We will conduct focus group interviews of staff to assess the usefulness of OPTIMAL after T3.
- 3. Describe resident outcomes (Exploratory).** We will measure and describe resident mealtime difficulties, eating performance, intake success rate, and body mass index using descriptive statistics over time for two treatment groups. Data obtained will inform estimates of effect sizes for a future larger-scale trial.

## Design

We used mixed methods (i.e., focus groups, a pilot single-group repeated measures) to refine and test OPTIMAL. We collected repeated measures at 3 time points: baseline (T1), immediately post intervention (6 weeks post baseline, T2), and 6-week post intervention (12 weeks post baseline, T3). At each time point, we assessed quality of staff engagement and resident outcomes including eating performance and BMI through collection and coding of videotaped observations of dyadic mealtime interaction (videos; Aim 2&3) over 6 meals in 2 consecutive days (2 breakfasts, 2 lunches, 2 dinners) for each staff-resident dyad. We used Cue Utilization and Engagement in Dementia (CUED) mealtime video coding scheme, an innovative, feasible, and reliable tool that our team has developed and validated, and assessed resident mealtime challenging behaviors including resistive behaviors and functional impairments and intake success rate using videos collected in this study.

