**OPTIMAL intervention (Aim 2 and 3).** A research assistant (OPTIMAL interventionist) will be trained by the PI to facilitate and implement the OPTIMAL intervention. To assure sustainability of OPTIMAL care, we will identify a staff champion (a staff participant who is a lead nursing assistant or licensed practical nurse) in each NH to work with the OPTIMAL interventionist during the intervention period. The interventionist will train all staff participants to implement OPTIMAL through 3 phases: I) one training session, II) ongoing mentoring to establish/refine PCMC plans, and III) two biweekly facilitations of OPTIMAL care delivery. Phases will be implemented sequentially, although they will overlap in that, once initiated, they will continue throughout the intervention period.

In Phase I, all staff participants from one NH will attend an in-person 2-hour group training session led by the OPTIMAL interventionist in the format of didactic lectures, role modeling/playing, practicing with each other, and demonstration and application of skills in

individualized PCMC care planning. All staff participants will be provided with training materials to be developed by completion of Aim 1 (see 4C4). If a staff is not able to attend the group session, we will record reasons of no attendance and schedule a make-up individual training session led by the interventionist. By completion of the training session, staff participants are expected to be able to 1) assess common mealtime difficulties and describe the use of targeted PCMC strategies, and 2) develop PCMC plans to address observed mealtime difficulties with targeted strategies. Staff will complete a PCMC-related knowledge and self-efficacy test to be developed based on training materials pre- and post-training session. Adequate receipt of the OPTIMAL training is indicated by a total test score of  $\geq 75\%$  post-training. Individual staff with a total test score of  $<75\%$  post-training will attend booster training sessions (in group or individual format) until the individual staff receive a total test score of  $\geq 75\%$ .

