The OPTIMAL interventionist will initiate Phase II, individualized PCMC planning, working closely with staff and resident participants. The interventionist will assess each resident's eating independence and mealtime difficulties as well as staff use of PCMC&TCMC strategies during the first week of the OPTIMAL intervention. After assessment, the interventionist will record major mealtime difficulties demonstrated by the resident, strategies used that do (not) work, and any barriers to implementing specific strategies. The interventionist will then develop a PCMC care plan for each resident by working with staff participants based on assessments of common mealtime difficulties. The primary goal is to engage residents to be actively involved in eating and initiate each intake attempt by themselves with minimum assistance using appropriate PCMC strategies. For example, a care plan for a resident demonstrating prolonged chewing may include offering food bites of smaller size, offering drinks frequently to flush food down, and giving short, simple verbal cues. Another example is that for a resident with difficulty using utensil properly, the care plan may include preloading utensils, offering finger food, and providing adaptive utensils. The interventionist will work with the staff participants to identify possible solutions to eliminate any barriers to implement specific PCMC strategies, the best places to store/locate the care plans, as well as the best way for staff participants to review residents' updated care plans in each NH.

After individualized PCMC care plans are established, Phase III, biweekly facilitations of OPTIMAL care, will be provided to each staff participant twice over 4 weeks by the OPTIMAL interventionist. The interventionist will coach staff participants in implementing care plans for resident participants. In each facilitation, the interventionist will observe each staff participant in providing care to a resident during one meal, and provide role modeling as well as feedback on how well the staff follows and implements the care plan. In this phase, individualized PCMC care plans will be updated continuously based on assessments of resident mealtime difficulties.

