**Usefulness of OPTIMAL.** Staff perceived usefulness of the OPTIMAL intervention (OPTIMAL group) or OPTIMAL training session (education control group) will be assessed using semi-structured focus group interviews. Open-ended questions focus on experiences in delivering OPTIMAL care, use of PCMC-related strategies, strategies that do (not) work, and suggestions of refinement for OPTIMAL (see Appendix 7).

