**Expected Outcomes and Impact for Future Trials.** *Using mixed methods, qualitative and quantitative data will be collected and analyzed to refine OPTIMAL intervention protocol, training materials, and study procedures, and to understand its feasibility, fidelity, and usefulness. Data obtained from this pilot trial will provide five critical pieces of information for a future larger efficacy trial. They are:* 1) refined OPTIMAL intervention protocol and training materials with preliminary evidence of feasibility, fidelity, and usefulness; 2) refined study procedures for recruitment, retention, data collection, and recording and behavioral coding of videos; 3) evidence of feasibility for a two-group parallel cluster RCT design with three repeated measures (baseline, 6- & 12-weeks post baseline); 4) effect size estimates of resident outcomes for sample size calculation; and 5) videotaped observations collected in this study to be used in future staff training sessions to illustrate OPTIMAL care skills.

**Limitations.** As a pilot RCT, a small sample of staff and residents from 4 NHs will be enrolled. This is a logical first step to develop and test a new behavioral intervention, prior to a large-scale efficacy trial.

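### The Design section describes a single-group pilot, but Aim 3, the Usefulness paragraph and the Limitations describe the same study as two-group, controlled or randomised

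*Combined protocol and SAP*

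**What the plan says.** The Design section gives the structure in one sentence: "We used mixed methods (i.e., focus groups, a pilot single-group repeated measures) to refine and test OPTIMAL". It then sets out three time points (baseline, 6 weeks and 12 weeks) and mentions no second group.

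The intervention section of Methods is written for everyone enrolled: "The interventionist will train all staff participants to implement OPTIMAL through 3 phases". It places a staff champion "in each NH to work with the OPTIMAL interventionist during the intervention period". In Phase II, "The interventionist will then develop a PCMC care plan for each resident by working with staff participants". In Phase III, every staff participant receives two facilitations over four weeks.

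The Aim 3 paragraph of the Statistical Analysis Plan lists descriptive summaries of the resident outcomes over time. It contains no group factor and no comparison.

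Three statements describe the study differently:

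- Objectives, Aim 3: resident outcomes will be described "using descriptive statistics over time for two treatment groups".
- Usefulness of OPTIMAL, under Aim 2: staff-perceived usefulness of the "OPTIMAL intervention (OPTIMAL group) or OPTIMAL training session (education control group) will be assessed" in focus groups.
- Limitations: "As a pilot RCT, a small sample of staff and residents from 4 NHs will be enrolled".

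Item 3 under Expected Outcomes and Impact for Future Trials lists, among the things this pilot will supply, "evidence of feasibility for a two-group parallel cluster RCT design with three repeated measures".

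**The concern.** The number of groups, and whether nursing homes (NHs) were randomised, decide what a pilot can conclude. As written, a reader cannot settle either from the document.

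If there was one group, the Aim 3 summaries describe change in that group. The study then cannot show that homes will accept randomisation, or that a control condition can be delivered and its participants retained, so item 3 of Expected Outcomes claims more than the data can give.

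If there were two groups, the analysis plan omits the by-group summaries that Aim 3 promises, and the document does not say how homes were allocated or how the control condition was delivered.

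**Working it through.** No sample size, allocation ratio or power figure is given, so there is nothing to recompute. The check is to compare every place that states the number of groups, the comparator or randomisation.

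1. **Explicit statement of one group.** There is one, in the Design section.

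2. **Text consistent with one group.** In the intervention section, all staff participants go through all three phases, each NH has a champion working with the interventionist, each resident has a care plan, and each staff participant has the facilitations. None of this is limited to one arm. The Aim 3 analysis paragraph summarises over time only.

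3. **Statements of two groups, a control or randomisation for this study.** There are three: Aim 3, the Usefulness paragraph and the Limitations.

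4. **Could the two sets be compatible?** The Usefulness paragraph is more than a stray label. It pairs the full intervention with one group and the training session with the other. The training session is Phase I of three, so a group receiving only that session cannot exist if all staff participants go through all three phases. A single-group study also cannot be an RCT.

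5. **Does anything resolve the conflict?** No amendment log or note marks either description as superseded. The document describes no randomisation procedure, unit or ratio of allocation, or control-condition delivery. Two PHS HSCTI sections are cited (2.5 for recruitment and retention, 4.4 for statistical design and power) but are not part of the document, so whether they cover this is unknown. Even if they do, the Design section would still disagree with the three statements.

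6. **Item 3 of Expected Outcomes.** This can be read as naming the design of the future trial, so it is not counted as a fourth contradiction. On the single-group reading it is only partly supported. One group can inform recruitment, consent, retention, training, video collection and the three-time-point schedule. It cannot inform randomisation of NHs or control-arm feasibility and retention.

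**The case against.** The strongest reply is that the document can largely be resolved from its own tenses. The Design section and the analysis plan report in the past tense what was done, and they agree with each other. The three conflicting statements are in the future tense. The focus groups show the same pattern: Aim 1 plans separate staff and family groups, while Methods reports a single stakeholder group. This looks like plan text that was not fully updated after the study was run.

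That makes one group the likelier reading, and it lowers the seriousness of the point. It remains an inference. The intervention section is also in the future tense yet fits a single group, as do the consent and data collection procedures, so future-tense text cannot simply be set aside as obsolete.

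A second reply is that Aim 3 is exploratory and descriptive, with no test and no efficacy conclusion planned, so no analysis is put at risk. On the single-group reading this stands in full. What is left is a design description that contradicts itself and a feasibility claim that is too broad.

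A reader might go further and infer that a randomised trial was run with its allocation and control arm left unreported. The document does not support that. Its procedures describe one group, and the cited sections that might describe allocation cannot be seen.

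A reader might also count how many of the 4 NHs could give control-arm information under each design. That figure appears only in the sentence calling the study a pilot RCT, which is itself in dispute, so shares built on it would not be reliable.

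**Conclusion.** The inconsistency is real, and the document is wrong as written: one explicit single-group statement, supported by the intervention and analysis sections, stands against three statements of two groups, a control group or an RCT. It should be corrected, but the likely correction is modest. On the single-group reading no planned summary changes, and the substantive effect is a narrower claim about cluster-RCT feasibility. That reading rests on the tense pattern and on the content of the intervention and analysis sections, not on any statement by the sponsor.

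A reader might also infer that the effect-size estimates for the future trial are presented as between-group effects. The document promises no between-group effect, and Aim 3 is labelled exploratory, so that is not part of this finding.

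**What to change.** First confirm how many groups and how many NHs the study had. Then reconcile the Design section, Aim 3, the Usefulness paragraph, and the Expected Outcomes and Limitations text.

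**If there was one group:**

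- Remove the two-group wording from Aim 3, the education-control wording from the Usefulness paragraph and the RCT label from the Limitations.
- Limit item 3 of Expected Outcomes to feasibility of recruitment, consent, retention, training, video collection and the three-time-point schedule.
- State there that randomisation of NHs, and control-arm feasibility and retention, were not tested.

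The cost is wording and a less favourable feasibility claim. The Aim 3 summaries stay as they are.

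**If there were two groups:**

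- Correct the Design section.
- Reconcile the intervention section with the control group named under Usefulness.
- State the allocation method and the control condition, or point to where the PHS HSCTI sections give them.
- Give the Aim 3 summaries by group.

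The cost is larger: several sections are corrected and by-group descriptive summaries are added.

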## Methods

**Development of OPTIMAL (Aim 1).** OPTIMAL is designed to teach staff to effectively manage mealtime difficulties and engage residents in eating to restore and maintain their highest level of function possible. We developed OPTIMAL following the four PCMC principles: 1) providing choices & acknowledging preferences (i.e., offering opportunities to make choices, providing and delivering food in ways personally acceptable and culturally appropriate), 2) supporting independence (i.e., providing appropriate technical, motivational, instrumental, and informational assistance based on residents' functional ability), 3) showing respect (i.e., honoring and valuing residents when assisting them), and 4) promoting social interactions (i.e., making connections with residents, creating/fostering a social environment with low stimuli and positive engagement). The use of these four PCMC principles in developing OPTIMAL is to manage *challenges that staff identified as the most significant barrier in providing optimal mealtime care in terms of assessing residents' preferences, interacting with residents, and modifying the over-stimulated environment.* While receiving formal and informal training in Year 1-2 of the K23, the PI developed OPTIMAL by integrating evidence from literature and our prior work. Specifically, the PI has conducted a systematic review synthesizing evidence on common mealtime difficulties and targeted behavioral strategies for residents with ADRD by searching five health-related electronic databases (Pubmed, CINAHL, AgeLine, PsychINFO, Cochrane Library) between 1990 and 2016. In this review, we have identified 98 unique mealtime difficulties categorized in four types of symptoms (behavioral, functional, cognitive, mixed), in which 48 mealtime difficulties are most commonly described and addressed by 260 unique behavioral multilevel strategies. The PI developed OPTIMAL intervention protocol and training materials following 3 steps: 1) updating evidence based on literature from 2017 forward; 2) integrating findings from the updated review, our preliminary studies (see 4C1), and our current R03 study that examines patterns of and temporal relationships between staff PCMC&TCMC behaviors and resident mealtime difficulties and intake (see 2A); and 3) synthesizing all the above evidence. The training materials will address three components of OPTIMAL: a) Why and What: rationale, benefits, and PCMC principles, b) How (basic): resident common mealtime difficulties and targeted behavioral multilevel PCMC strategies; and c) How (advanced): establishment of individualized PCMC plans based on assessments of common mealtime difficulties and use of targeted multilevel PCMC strategies.

**Evaluation and Refinement of OPTIMAL (Aim 1).** After the intervention protocol and training materials are developed, we conducted one focus group of NH stakeholders including leadership, staff, and families to prioritize the multiple mealtime difficulties identified from literature and to understand the acceptability of the OPTIMAL intervention following an interview guide. The focus

group was audio-recorded, and facilitated by the PI experienced in conducting focus group interviews. Data obtained were analyzed and used to refine the intervention protocol and training materials before pilot testing.

**Inclusion/Exclusion Criteria (Aim 2 and 3).** Participants including staff, residents, and families were recruited from nursing homes. Staff are eligible if they are 18 years old or above, English speaking, a permanent facility employee, provide informed consent, and provide direct mealtime care for a resident participant at least twice a week over the previous month. Families are eligible if they are 18 years old or above, English speaking, a family member of the resident who is living at the NH study site at the time of the study, having experiences of delivering mealtime care to their resident family members, and providing informed consent.

Residents are eligible if they: 1) are  $\geq 55$  years, 2) diagnosed as having ADRD based on medical records, 3) identified by NH staff as requiring mealtime assistance, and 4) having a legally authorized representative (LAR) providing informed written consent. Whether the resident needs mealtime assistance is based on medical record review as well as proxy report from the NH staff who has recently cared for the resident at mealtimes using the “feeding” item of the Katz ADL Index. Specifically, residents who need varied levels of assistance with feeding (limited, extensive, total assistance) are eligible, and those who get food from plate into mouth without help are excluded regardless of who prepares food. Residents will be excluded if they: 1) have a documented diagnosis of Parkinson’s disease, traumatic brain injury, or swallowing disorder, 2) do not eat orally (e.g., parenteral/IV feedings, use of feeding tubes), 3) unable to hear or see staff even with glasses and/or hearing aids (e.g., uncorrected visual or hearing impairment), or 4) stay in the NH study site for less than 12 weeks at the time of recruitment/consent/assent (e.g., terminally ill receiving hospice services, and/or receiving post-hospital skilled rehabilitation) that may not allow enough time for obtaining consent/assent, and scheduling days for video recording sessions across three time points (baseline, and 6- and 12-weeks post baseline).

**Recruitment and Consent (Aim 2 and 3).** To enroll staff and families, we will adapt a standard consent protocol for NH dementia mealtime research developed based on our prior study. To enroll residents, we will use a consent& assent protocol for research involving NH residents with dementia and their legally authorized representatives (LARs). Briefly, proxy informed consent will be obtained from the eligible resident’s LAR, and assent from the resident afterwards. Detailed plan is described in the [PHS HSCTI, 2.5 Recruitment and Retention Plan](#).

**OPTIMAL intervention (Aim 2 and 3).** A research assistant (OPTIMAL interventionist) will be trained by the PI to facilitate and implement the OPTIMAL intervention. To assure sustainability of OPTIMAL care, we will identify a staff champion (a staff participant who is a lead nursing assistant or licensed practical nurse) in each NH to work with the OPTIMAL interventionist during the intervention period. The interventionist will train all staff participants to implement OPTIMAL through 3 phases: I) one training session, II) ongoing mentoring to establish/refine PCMC plans, and III) two biweekly facilitations of OPTIMAL care delivery. Phases will be implemented sequentially, although they will overlap in that, once initiated, they will continue throughout the intervention period.

In Phase I, all staff participants from one NH will attend an in-person 2-hour group training session led by the OPTIMAL interventionist in the format of didactic lectures, role modeling/playing, practicing with each other, and demonstration and application of skills in

individualized PCMC care planning. All staff participants will be provided with training materials to be developed by completion of Aim 1 (see 4C4). If a staff is not able to attend the group session, we will record reasons of no attendance and schedule a make-up individual training session led by the interventionist. By completion of the training session, staff participants are expected to be able to 1) assess common mealtime difficulties and describe the use of targeted PCMC strategies, and 2) develop PCMC plans to address observed mealtime difficulties with targeted strategies. Staff will complete a PCMC-related knowledge and self-efficacy test to be developed based on training materials pre- and post-training session. Adequate receipt of the OPTIMAL training is indicated by a total test score of  $\geq 75\%$  post-training. Individual staff with a total test score of  $<75\%$  post-training will attend booster training sessions (in group or individual format) until the individual staff receive a total test score of  $\geq 75\%$ .

The OPTIMAL interventionist will initiate Phase II, individualized PCMC planning, working closely with staff and resident participants. The interventionist will assess each resident's eating independence and mealtime difficulties as well as staff use of PCMC&TCMC strategies during the first week of the OPTIMAL intervention. After assessment, the interventionist will record major mealtime difficulties demonstrated by the resident, strategies used that do (not) work, and any barriers to implementing specific strategies. The interventionist will then develop a PCMC care plan for each resident by working with staff participants based on assessments of common mealtime difficulties. The primary goal is to engage residents to be actively involved in eating and initiate each intake attempt by themselves with minimum assistance using appropriate PCMC strategies. For example, a care plan for a resident demonstrating prolonged chewing may include offering food bites of smaller size, offering drinks frequently to flush food down, and giving short, simple verbal cues. Another example is that for a resident with difficulty using utensil properly, the care plan may include preloading utensils, offering finger food, and providing adaptive utensils. The interventionist will work with the staff participants to identify possible solutions to eliminate any barriers to implement specific PCMC strategies, the best places to store/locate the care plans, as well as the best way for staff participants to review residents' updated care plans in each NH.

After individualized PCMC care plans are established, Phase III, biweekly facilitations of OPTIMAL care, will be provided to each staff participant twice over 4 weeks by the OPTIMAL interventionist. The interventionist will coach staff participants in implementing care plans for resident participants. In each facilitation, the interventionist will observe each staff participant in providing care to a resident during one meal, and provide role modeling as well as feedback on how well the staff follows and implements the care plan. In this phase, individualized PCMC care plans will be updated continuously based on assessments of resident mealtime difficulties.

**Data Collection Procedures (Aim 1, 2, 3; Table 1).** In each NH, immediately after written consents of staff and family participants are obtained, separate focus groups for staff and families will be scheduled and conducted (see 4C4b, Aim 1), and participants' characteristics will be collected using a demographic survey (4C7) before T1. Residents will be recruited with written assents/consents from residents and their LARs. Resident characteristics will be collected by reviewing medical records. Feasibility data about identification, recruitment, consent, and retention of all participants will be gathered throughout the study (see 4C8a, Aim 2). A trained research videographer will schedule a 1-day practice recording session for each resident participant using a mini handheld digital video recorder. Adequate quality recordings for behavioral analyses have been obtained with a mini digital camera in prior research. After the practice session, the videographer will schedule a 2-day formal recording session for each resident participant at baseline (T1), and at 6- (T2) and 12-week post baseline (T3), respectively (Aim 2&3). We will videotape mealtime only in the scheduled days of all recording sessions. Staff participants will complete a knowledge & self-efficacy test pre- and post- OPTIMAL training

sessions (Aim 2). At each time point, in addition to mealtime video recording, a trained data collector will collect body mass index (BMI) of each resident, and complete observational measures on quality of staff engagement and resident eating performance for each of the 6 meals in 2 days in the NH (Aim 2&3). After T3, we will conduct one focus group in each NH (Aim 3), lasting 50-60 minutes, audio-recorded, and facilitated by the PI experienced in focus group interviews.

